TTD will be calculated as the duration between the start of a treatment line to the end of the treatment line for patients with discontinuation of treatment for any reason, or censoring if a stop date is not documented (at end of study), if the patient dies, is lost-to follow up, or is still on-therapy. Patients without a discontinuation event will be censored on the study end date or at last office visit date without clinical or radiographic evidence of progression, whichever occurred first. Time to TTD will be analysed using the Kaplan-Meier method with 95% CIs, and summary tables of the number of events and censored patients at each month interval included.

Durable response rate (DRR)

DRR will be determined as the proportion of patients with objective response (CR or PR) with a duration of at least 6 months. Duration of response will be calculated as previously defined for DOR.

Time-to-Event Analysis

The Kaplan-Meier method will be used to estimate median OS, PFS and TTD. P values comparing survival curves by stratification groups, will be calculated using log-rank tests. Univariate and multivariable Cox proportional hazards regressions will be used to evaluate explanatory factors and to calculate hazard ratios (HRs) with two-sided 95% CIs for OS, PFS and TTD. Demographic and clinical factors will be included in multivariable Cox regression models based on their clinical relevance and/or the univariate significance level (assessed at the level of $p < 0.05$).

In order to account for the impact of baseline patient and disease characteristics outlined in this protocol and the disease characteristics below, unadjusted Cox models and multivariable Cox models adjusting for selected patient demographics and clinical characteristics identified by Pfizer as clinically relevant will be included in the adjusted models. Time-to-event analyses will be assessed in the overall population and by stratifications of interest (MSKCC/IMDC category). The disease characteristics of interest are:

- a. Less than one year from time of diagnosis;
- b. Karnovsky performance status less than 80%;
- c. Haemoglobin less than the lower limit of normal (eg, less than 12 g/dl);
- d. Serum calcium greater than the upper limit of normal (eg, 10 mg/dl or: 2.5 mmol/l);
- e. Neutrophil greater than the upper limit of normal (eg, greater than 7.0×10^9 dl);
- f. Platelets greater than the upper limit of normal (eg, greater than 400 000);

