ANNEX 2. ADDITIONAL INFORMATION

1. MSKCC Criteria.¹

Patients are stratified according to the presence of five risk factors:

- KPS <80%;
- Time from diagnosis to start of systemic therapy <12 months;
- Haemoglobin < lower limit of laboratory's reference range;
- Lactate dehydrogenase $1.5 \times$ the upper limit of laboratory's reference range;
- Corrected serum calcium >10.0 mg/dl (2.4 mmol/l).

The number of risk factors present is added up and the risk is stratified as follows:

Number of risk factors	Risk group
0	Favourable
1-2	Intermediate
3-5	Poor

2. IMDC (Heng) Criteria.²

Patients are stratified according to the presence of six risk factors:

- Karnovsky performance status (PS) <80%;
- Haemoglobin less than lower limit of normal;
- Time from diagnosis to treatment <1 year;
- Corrected calcium above the upper limit of normal;
- Platelets greater than the upper limit of normal;
- Neutrophils greater than the upper limit of normal.

The number of risk factors present is added up and the risk is stratified as follows:

Number of risk factors	Risk group
0	Favourable
1–2	Intermediate
3–6	Poor

3. ECOG performance status.³

GRADE	ECOG PERFORMANCE STATUS
0	Fully active, able to carry on all pre-disease performance without restriction
1	Restricted in physically strenuous activity but ambulatory and able to carry out work of a light or sedentary nature, eg, light house work, office work
2	Ambulatory and capable of all selfcare but unable to carry out any work activities; up and about more than 50% of waking hours
3	Capable of only limited selfcare; confined to bed or chair more than 50% of waking hours
4	Completely disabled; cannot carry on any selfcare; totally confined to bed or chair
5	Dead

4. Fuhrmann grade.⁴

Pathologic material was classified as to pathologic stage, tumor size, cell arrangement, cell type and nuclear grade. Four nuclear grades (1--4) were defined in order of increasing nuclear size, irregularity and nucleolar prominence. Nuclear grade was more effective than each of the other parameters in predicting development of distant metastasis following nephrectomy.

5. TNM stage.⁵

Staging of RCC (UICC TNM classification of malignant tumors, 7th edition, 2009).

T	Primary tumor
TX	Primary tumor cannot be assessed
T0	No evidence of primary tumor
T1	Tumor ≤ 7 cm in greatest dimension, limited to the kidney
T1a	Tumor ≤ 4.0 cm
T1b	Tumor >4.0 cm but ≤ 7.0 cm
T2	Tumor >7.0 cm in greatest dimension, limited to the kidney

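### Cox models of a risk score's own components, if fitted within the MSKCC/IMDC categories those components define, give hazard ratios pulled towards or past 1; section 9.7 should rule out the univariate and partly adjusted versions

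*Combined protocol and SAP*

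**What the plan says.** Under Time-to-Event Analysis, section 9.7 first covers Kaplan-Meier medians and group comparisons: "P values comparing survival curves by stratification groups, will be calculated using log-rank tests". It then plans regression for OS, PFS and TTD: "Univariate and multivariable Cox proportional hazards regressions will be used to evaluate explanatory factors". Covariate entry is flexible: "Demographic and clinical factors will be included in multivariable Cox regression models based on their clinical relevance and/or the univariate significance level", with the univariate level set at p<0.05. The next paragraph describes unadjusted models and models adjusted for a selected set of characteristics, states "Time-to-event analyses will be assessed in the overall population and by stratifications of interest (MSKCC/IMDC category"), and goes straight on to factors a to i.

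Annex 2 builds both scores from that list. MSKCC uses five factors (a, b, c, d, g) and IMDC uses six (a to f). For each, "The number of risk factors present is added up and the risk is stratified as follows": 0 is favourable, 1-2 intermediate, 3 or more poor. Fuhrmann grade (h) and tumour subtype (i) belong to neither score.

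Nothing in the document limits by-category work to Kaplan-Meier and log-rank, or removes a score's components from within-category Cox models. The only limit on subgroup reporting is a size condition under Descriptive Analysis. The baseline list in section 9.7 allows either score or both, so which factors lie inside the stratifying score is not settled.

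**The concern.** Secondary objective 5 (section 8) asks which factors, including the individual score parameters, predict TTD. If component models are also run within categories, the grouping variable is a function of the covariate under study. Holding the count within a band forces a trade-off: a patient with one component has less room for the others. A hazard ratio that does not adjust for all the others absorbs that trade-off.

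The practical risk is contradictory output: a factor predictive in the whole cohort but null or reversed within a risk group, for reasons of arithmetic rather than biology. The p<0.05 screen is not confined to the overall cohort. Applied within a category it could drop real factors and leave the partly adjusted models that carry the distortion.

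**Working it through.** The plan gives no power, event or effect figure to reproduce. Its inputs are the Annex 2 count definitions and the approximate totals in section 9.5: 678 patients on sunitinib and 163 on axitinib. Those totals are not split by line, so they are upper bounds for the analysis cohorts. Prevalences, hazard ratios, correlations and event fractions below are assumptions.

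**Step 1. Structure.** With count 1-2, a carrier of a component has 0 or 1 of the others and a non-carrier has 1 or 2. This needs no assumption.

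**Step 2. Mean number of other components** (independent components, prevalence p = 0.3).

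- MSKCC, four others: P(0) = 0.2401, P(1) = 0.4116, P(2) = 0.2646.
- Intermediate, carriers: 0.4116/(0.2401 + 0.4116) = 0.63.
- Intermediate, non-carriers: (0.4116 + 2 × 0.2646)/(0.4116 + 0.2646) = 1.39.
- IMDC, five others: 0.68 and 1.46.
- Over p = 0.2 to 0.4 and both scores: 0.50-0.77 against 1.27-1.57.
- MSKCC poor group, with P(3) = 0.0756 and P(4) = 0.0081: carriers (two or more others) 0.7884/0.3483 = 2.26; non-carriers (three or more) 0.2592/0.0837 = 3.10.

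**Step 3. Effect on a univariate hazard ratio.** Approximation: apparent log HR = true log HR − (difference in other components) × (mean log HR of the others). For MSKCC, intermediate, the difference is 1.39 − 0.63 = 0.76. Assume component HRs 1.3, 1.3, 1.5, 1.5 and 2.0.

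| True HR | Geometric mean HR of the others | Apparent HR |
|---|---|---|
| 1.3 | 1.56 | 1.3 × 1.56^(−0.76) = 0.93 |
| 1.5 | 1.50 | 1.5 × 1.50^(−0.76) = 1.10 |
| 2.0 | 1.40 | 2.0 × 1.40^(−0.76) = 1.55 |

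**Step 4. Simulation.** Exponential survival, both scores, prevalence 20-40%, latent correlation 0 or 0.3, 50-95% events, same HR mix (a third 1.5 added for IMDC).

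| Setting | True HR | Median fitted HR | HR>1 with p<0.05 |
|---|---|---|---|
| N=678, intermediate, univariate | 1.3 | 0.92-0.97 | 0-2% |
| N=678, intermediate, univariate | 1.5 | 1.07-1.12 | 7-15% |
| N=678, intermediate, univariate | 2.0 | 1.50-1.57 | 65-96% |
| N=678, intermediate, partly adjusted (two other components) | 1.5 | 1.12-1.18 | 11-32% |
| N=678, intermediate, all components | 1.5 | 1.47-1.53 | – |
| N=678, poor, univariate | 1.5 | 1.01-1.27 | – |
| N=163, intermediate, univariate | 1.5 | 1.07-1.13 | 4-7% |

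In the overall cohort at N=678, a true 1.5 reaches p<0.05 univariately in 87-100% of runs. A factor outside the score (true 1.5) appears as 1.45-1.64 in the intermediate group, so the effect is specific to components. A second set of assumptions (prevalence 0.15-0.55, HRs 1.4-1.9, correlation 0-0.5) gave the same pattern: in the intermediate group a true 1.4 appeared as 0.93-1.00 univariately and 1.36-1.43 with all components.

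**Step 5. Poor group and correlation.** Six components, prevalence 0.4, other components held by carriers and non-carriers: 2.62 v 3.31 at latent correlation 0; 3.22 v 3.51 at 0.3; 3.59 v 3.60 at 0.5; 3.97 v 3.67 at 0.7. The effect shrinks, vanishes, then reverses. In the intermediate group it persists throughout (0.61 v 1.38 at 0.7).

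**Step 6. Favourable group.** A count of 0 means every component is absent, so no component HR exists, provided category and component values coincide. The document does not secure this. The risk grade is a recorded variable (section 9.3), re-scoring at second line is not stated, and calcium is defined two ways: "Serum calcium greater than the upper limit of normal (eg, 10 mg/dl or: 2.5 mmol/l") in section 9.7 and "Corrected serum calcium >10.0 mg/dl (2.4 mmol/l") in Annex 2. If 5%, 10% or 20% of component values differ from those behind the category, a true 1.5 in the intermediate group appears as 1.16, 1.22 or 1.30-1.32, and the favourable group then holds on average about 1.5 to 6 carriers per component.

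**The case against.** **The sentence may mean only Kaplan-Meier and log-rank.** It does not mention Cox, and pairing the overall population with risk category is how section 9.7 introduces the PFS and OS curves. Secondary objective 2 for each line also needs TTD by MSKCC risk, and the TTD paragraph does not provide it, so the sentence has a job to do on this reading. This stands: the Cox reading is likely from its position, not certain.

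**The distorted models are permitted, not prescribed.** Entry on clinical relevance would allow a model with all components, which recovers the true values. This stands, and is why the point is confined to univariate and partly adjusted models.

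**Overall-cohort univariate hazard ratios also miss the conditional value.** With correlated components, a true 1.5 appears there as 1.93-2.16. This is correct, but it is ordinary confounding between components, which joint adjustment addresses. It is not created by the grouping.

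**The study is descriptive.** A within-group univariate hazard ratio is a valid description of that group. However, the plan asks which factors predict TTD and attaches confidence intervals and a p-value screen, and readers will take the figures as factor effects.

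**Stronger readings.** A reader might infer that the same distortion always holds in the poor group, that objective 5 cannot be answered, or that components must never be modelled within a category. Step 5 contradicts the first. Overall-cohort models answer objective 5. All-component models within the intermediate and poor groups avoid the distortion.

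**Conclusion.** The point holds in a limited form. On the likely reading of section 9.7, univariate and partly adjusted Cox models of a score's components would be fitted within categories defined by counting those components.

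- **Intermediate group:** the imbalance follows from the definition. Its size (0.63 v 1.39 other components; a true 1.5 seen as about 1.1) rests on assumed prevalences and hazard ratios, and shrinks if recorded categories and component values disagree. Weak and moderate factors suffer most; one strong factor (HR 2.0) among weaker ones usually survives at N=678.
- **Poor group:** the same occurs at low to moderate correlation between components, but it can vanish or reverse at high correlation.
- **Favourable group:** the hazard ratio is not estimable when the values coincide.

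The document does not support a claim that the main results are compromised. PFS by category is unaffected, and the overall-cohort models are free of this conditioning. The change is worth making because the harm is avoidable and the text excludes neither reading.

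**What to change.** Add one paragraph to Time-to-Event Analysis in section 9.7:

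- Univariate and selected-covariate Cox models of a score's own components are fitted for OS, PFS and TTD in the overall cohort of each line only, with risk category in a separate model.
- By-category output consists of Kaplan-Meier estimates for OS, PFS and TTD, the log-rank test between categories, and Cox models of factors outside the stratifying score: grade and subtype for both; neutrophils and platelets for MSKCC; LDH for IMDC.
- If component hazard ratios within the intermediate or poor group are wanted, they come only from a model with all of that score's components and no univariate p<0.05 screen, with a note on low precision for axitinib. At N=163, a true 1.5 reaches p<0.05 in 15-31% of runs in the intermediate group.
- The stratifying score is named for each analysis.

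This needs no new data and means fewer by-category models. If only Kaplan-Meier and log-rank were intended, the paragraph records that. What is given up is univariate and partly adjusted component results within categories.

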9.8. Quality Control

The data collection tool is an Microsoft Access database. The investigators have entered pseudo-anonymized data directly from patient charts/electronic records into the database, which will have a function to directly export the collected data into an Excel/CSV file. Therefore the data collection tool will also serve as a project database (once exported into Excel).

Review of the patient records was to be conducted by a carefully selected team of physicians and/or their assigned staff trained on the study specific protocols and guidelines. Physicians and/or site staff will be instructed to assign a unique identifier for each patient enrolled in the study to facilitate follow-up on data queries and for data validation.

The Data Collection Manager/Team Lead will review pilot data for accuracy and consistency. During full chart review, the Data Collection Manager/Team Lead will perform random checks. During both the pilot and full chart review, the study's Principal Clinical Investigator addresses clinical questions posed by the chart review team. The Data Collection Manager will also initiate normalization of data, quality control all charts, and review of the final data set before submission to the sub-study team.

Finally, the principal investigator and statistical lead will provide a final examination of the data before and during preparation of analyses.

The principal investigator will create the CT24 Study Data Quality Control plan.

9.9. Strengths and Limitations of the Research Methods

This is a large scale retrospective non-interventional RWD study. The strengths of this methodology include:

- A representative impression of the real world use and activity of medicines is obtained;
- Patients who may not be eligible for randomized controlled trials can be included;
- Retrospective nature mitigates bias in regard to treatment selection and outcome monitoring.

Potential limitations of this study design are:

- Compliance issues eg, missed doses, treatment breaks, schedule modifications may not be captured in detail;
- The place of real world studies in the hierarchy of medical evidence levels is not fully understood;
- Retrospective studies can detect associations, but not causality;
- Data are collected on a voluntary basis (convenience sampling) without any requirement in terms of sample design and stratifications;
- There could be errors in data entry that are unaccounted for, and which represent information bias. This cannot be controlled in the analysis.

In the analysis, all steps taken by the study team will be auditable. The protocol has been written very specifically, in order that the research objectives and methods are open and transparent.

9.10. Other Aspects

Not applicable.

10. PROTECTION OF HUMAN SUBJECTS

10.1. Patient Information

All parties will comply with all applicable laws, including laws regarding the implementation of organizational and technical measures to ensure protection of patient personal data. Such measures will include omitting patient names or other directly identifiable data in any reports, publications, or other disclosures, except where required by applicable laws.

The personal data will be stored at the study site in encrypted electronic and/or paper form and will be password protected or secured in a locked room to ensure that only authorized study staff have access. The study site will implement appropriate technical and organizational measures to ensure that the personal data can be recovered in the event of disaster. In the event of a potential personal data breach, the study site shall be responsible for determining whether a personal data breach has in fact occurred and, if so, providing breach notifications as required by law.

To protect the rights and freedoms of natural persons with regard to the processing of personal data, when study data are compiled for transfer to Pfizer and other authorized parties, patient names will be removed and will be replaced by a single, specific, numerical code, based on a numbering system defined by Pfizer. All other identifiable data transferred to Pfizer or other authorized parties will be identified by this single, patient-specific code. The investigator site will maintain a confidential list of patients who participated in the study, linking each patient's numerical code to his or her actual identity. In case of data transfer,

Pfizer will maintain high standards of confidentiality and protection of patients' personal data consistent with the clinical study agreement and applicable privacy laws.

10.2. Patient Consent

As this study does not involve data subject to privacy laws according to applicable legal requirements, obtaining informed consent from patients by Pfizer is not required.

10.3. Institutional Review Board (IRB)/Independent Ethics Committee (IEC)

Research Ethics Committee (REC) approval has been sought in the UK. The Integrated Research Application System (IRAS) number for this study is: 266899 and the REC number is 19/LÖ/1041. No data will be transferred until this approval has been granted.

10.4. Ethical Conduct of the Study

The study will be conducted in accordance with legal and regulatory requirements, as well as with scientific purpose, value and rigor and follow generally accepted research practices described in Guidelines for Good Pharmacoepidemiology Practices (GPP) issued by the International Society for Pharmacoepidemiology (ISPE), Good Epidemiological Practice (GEP) guidelines issued by the International Epidemiological Association (IEA), Good Practices for Outcomes Research issued by the International Society for Pharmacoeconomics and Outcomes Research (ISPOR), International Ethical Guidelines for Epidemiological Research issued by the Council for International Organizations of Medical Sciences (CIOMS), EMA European Network of Centres for Pharmacoepidemiology and Pharmacovigilance (ENCePP) Guide on Methodological Standards in Pharmacoepidemiology, and FDA Guidance for Industry: Good Pharmacovigilance and Pharmacoepidemiologic Assessment, FDA Guidance for Industry and FDA Staff: Best Practices for Conducting and Reporting of Pharmacoepidemiologic Safety Studies Using Electronic Healthcare Data Sets, Guidance for Industry: Patient-Reported Outcome Measures: Use in Medical Product Development to Support Labeling Claims and/or equivalent.

11. MANAGEMENT AND REPORTING OF ADVERSE EVENTS/ADVERSE REACTIONS

11.1. Structured Data Analysis

This study involves data that exist as structured data by the time of study start.

In these data sources, individual patient data are not retrieved or validated, and it is not possible to link (ie, identify a potential association between) a particular product and medical event for any individual. Thus, the minimum criteria for reporting an adverse event (AE) (ie, identifiable patient, identifiable reporter, a suspect product, and event) cannot be met.

11.2. Human Review of Unstructured Data

This study protocol requires human review of patient-level unstructured data; unstructured data refer to verbatim medical data, including text-based descriptions and visual depictions of medical information, such as medical records, images of physician notes, neurological scans, X-rays, or narrative fields in a database.

The reviewer is obligated to report adverse events (AEs) with explicit attribution to any Pfizer drug that appear in the reviewed information (defined per the patient population and study period specified in the protocol). Explicit attribution is not inferred by a temporal relationship between drug administration and an AE, but must be based on a definite statement of causality by a healthcare provider linking drug administration to the AE.

The requirements for reporting safety events on the non-interventional study (NIS) adverse event monitoring (AEM) Report Form to Pfizer Safety are as follows:

- All serious and non-serious AEs with explicit attribution to **any Pfizer drug** that appear in the reviewed information must be recorded on the Non-interventional Study Adverse Event Report Form (see [Annex 1](#)) and reported, within 24 hours of awareness, to Pfizer Safety using the NIS AEM Report Form.
- Scenarios involving drug exposure, including exposure during pregnancy, exposure during breast feeding, medication error, overdose, misuse, extravasation, lack of efficacy, and occupational exposure associated with the use of a Pfizer product must be reported, within 24 hours of awareness, to Pfizer Safety using the NIS AEM Report Form.

For these AEs with an explicit attribution or scenarios involving exposure to a Pfizer product, the safety information identified in the data reviewed is captured in the Event Narrative section of the report form, and constitutes all clinical information known regarding these AEs. No follow-up on related AEs will be conducted.

All the demographic fields on the NIS AEM Report Form may not necessarily be completed, as the form designates, since not all elements will be available due to privacy concerns with the use of secondary data sources. While not all demographic fields will be completed, at the very least, at least one patient identifier (eg, gender, age as captured in the narrative field of the form) will be reported on the NIS AEM Report Form, thus allowing the report to be considered a valid one in accordance with pharmacovigilance legislation. All identifiers will be limited to generalities, such as the statement “A 35-year-old female...” or “An elderly male...” Other identifiers will have been removed.

Additionally, the onset/start dates and stop dates for “Illness”, “Study Drug”, and “Drug Name” may be documented in month/year (mmm/yyyy) format rather than identifying the actual date of occurrence within the month/year of occurrence in the day/month/year (DD/MMM/YYYY) format.

All research staff members must complete the following Pfizer training requirements:

- *“YRR Training for Vendors Working on Pfizer Studies (excluding interventional clinical studies and non-interventional primary data collection studies with sites/investigators)”*.

These trainings must be completed by research staff members prior to the start of data collection. All trainings include a “Confirmation of Training Certificate” (for signature by the trainee) as a record of completion of the training, which must be kept in a retrievable format. Copies of all signed training certificates must be provided to Pfizer.

